#### 8.3 Other Assessments

#### 8.3.1 Quality of Life

Quality of life assessments of the patient will be conducted via paper-based questionnaires and quality of life sheets or by electronic devices (for example: iPads or other secure mobile devices) directly entered onto an online platform by the patients/carers. If necessary the RN/member of the research team will provide guidance on how to complete the questionnaires and will collect them/the electronic device from the patients and carers at the end of the study visits.

The following quality of life questionnaires will be administered to the patient and/or parent/guardian:

#### **DLQI**

To be completed by all patients who are above 16 years.

#### **CDLQI**

To be completed by the patient (4 years - 16 years) during the visit. There is no difference between the questions of either the CDLQI - older children and the CDLQI - with cartoons. The researcher should assess which CDLQI questionnaire will be most appropriate for each individual child.

#### **IDQOL**

To be completed by the parent/guardian for patients who are below the age of 4 years during the visit.

#### EQ-5D-5L (adults) and EQ-5D-Y (children)

These generic quality of life scores will be completed by all patients or parents/guardian as indicated in the Study Schedule. The EQ-5D-Y is designed/validated for age 8-15 years only. There is a proxy version, which is designed for children without capacity and guidance advises that can be used for 4-7-year olds.

#### 8.3.2 Health economics

There are two stages for the health economic investigations:

- 1. Pilot Phase: Information relating to the health economic component of the study, such as GP visits and attendance at other healthcare professionals, include required time off school or work, due to patients' atopic eczema will be gathered via the eCRF. This will allow us to assess the most relevant healthcare resource utilisation items for participants to record their healthcare contacts and which patient reported health-related quality of life instruments are most appropriate (particularly in the paediatric population). In order to identify the most efficient health economics data collection design, we will explore the feasibility of comparing direct patient reported data versus routine data linkage strategies (e.g. CPRD and HES) versus a mixture of the two. We will evaluate the cost, quality, accuracy and completeness of these data collection strategies for healthcare resource utilisation and health-related quality of life data collected prospectively via the eCRF. Furthermore, we will assess which of these strategies is best to estimate mean costs and patient reported health-related quality of life (including the EQ-5D data, the health benefit measure preferred by NICE) during the study period and for each eczema treatment option. Finally, our results will be used to identify a (health economics) core outcomes set for the assessment of eczema therapies, which can guide the design of the health economics component of future RCTs in eczema.
- 2. Post-Pilot Phase: These data will facilitate the cost-effectiveness assessment of alternative treatment strategies in the patient population recruited in the registry. Long term follow up data will be needed to develop a model-based health economics model describing the disease prognosis, the main clinical events experienced by patients, and associated costs and health related quality of life (HRQoL) implications. This

model will be used to generate costs and quality-adjusted life-years (QALYs). Statistical methods will be used to analyse the data collected in the registry and to account for the non-randomised study design. The model will be stochastic to reflect parameter and structural uncertainty surrounding our knowledge of the disease process and the impact of alternative therapies on patients' health status, health related quality of life (HRQoL) and healthcare contacts. Probabilistic sensitivity analysis (PSA), will be used to propagate parameters uncertainty through the model and to quantify their effect on the costs and HRQoL outcomes. The perspective for both analyses will be that of the NHS and Social Services for England and Wales. Life expectancy, costs and HRQoL will be discounted at 3.5% following NICE guidelines. More details will be provided in the health economics analysis plan, once additional funding for these analyses has been secured.

#### 8.3.3 Research laboratory assessments for the Biorepository

Laboratory specimens will be collected from patients who give specific consent for this optional research, and this work will only be done at selected sites with the resources and expertise to take and process such samples.

Patients/parents/guardians will have the option to select which additional samples to provide. For example, they may opt into additional blood tests as these coincide with blood draws already needed for safety monitoring, but opt out of any of the skin samples. Adults will be invited to provide up to a maximum of 70 ml of venous blood at each of the 4 study visits, while paediatric blood volumes (patients up to 16 years of age) will be strictly kept in line with international recommendations and are based on body weight.

The main aims of the building of a biorepository are to study the association of biomarkers with drug effectiveness, adverse events, and disease progression and to increase our molecular and genetic mechanistic understanding of atopic eczema pathogenesis.

The collection of samples for the Biorepository will be only commence when the Laboratory manuals/SOPs and logistical processes are in place, as decided by the SMG and communicated to the study participating sites by the SCC.

#### 8.3.3.1 All sites

#### **Genetic analyses**

We will collect venous blood for genetic markers. The mutational analyses will be conducted in [name] laboratory in Dundee, or another equally qualified laboratory.

In exceptional circumstances, where blood collection for genetic is not feasible (such as in the case of a recent blood transfusion), saliva sampling may be collected. A total of 2mls of saliva will be collected as per laboratory manual instructions.

All study participating centres can participate in the collection of genetic samples following patient's optional consent. Only one sample will be required, which can be collected at any time.

#### 8.3.3.2 Selected sites

Only selected sites will participate in the collection of some or all of the following biological samples:

#### **Biomarker analyses**

Where patients opt into the voluntary bioresource and mechanistic sample collection, venous blood will be collected to obtain serum for metabolic work and biomarker analyses relating to cutaneous and inflammatory disease (e.g. periostin), as well as to isolate and cryopreserve PBMCs for Immunophenotyping.

Blood samples will be collected at baseline, 4 weeks, 16 weeks and 12 months (or at different timepoints if decided by the SMG or SSC upon emerging evidence) using standard phlebotomy techniques.

#### **Epigenetics**

Blood will be collected for epigenetics analyses.

#### Measures of drug exposure (PKs)

Poor concordance with therapy, intra-individual variation and development of drug antibodies in drug pharmacokinetics are known to impact on treatment response. The following samples will therefore be collected at bioresource centres **depending on therapy prescribed**, to ascertain drug levels in participants at baseline and three follow up visits:

- Methotrexate: Patients on methotrexate will provide whole blood for methotrexate polyglutamates.
- **Biological drug levels:** Patients on biologic treatment will provide blood for metabolites and anti-drug antibodies (ADA).

If a participant is due a follow up, the time of last dosing and interruptions in treatment must be recorded.

#### Skin biopsies and tape strip collection:

Tape strip skin samples can be collected in participants of all ages, and skin biopsies in those ≥16 years of age (≤ 5mm punch) will be taken on 3 occasions both from involved and uninvolved skin for various analyses such as expressed cytokine, RNA, and immunochemical assessment of atopic eczema. The time points of the skin sample collection are subject to change if decided by the SMG or SSC upon emerging evidence.

Not all participating sites will be involved in the collection of skin biopsies and tape strip samples.

#### Skin microbiome

Skin microbiome samples for bacterial DNA extraction, next generation or shotgun sequencing to identify bacteria or other micro-organisms (such as viruses and fungi) will be taken. This sampling method is non-invasive and will be collected through a skin swab.

Recallability: Where patients consent to be contacted for further research, such as molecularly stratified randomised control trials, the Study Co-ordinating Centre will be able to identify participants with specific genetic mutations or biomarkers. Lab researchers will not have access to patients' medical information or any personal identifiable data.

#### 8.3.3.3 Laboratories for sample analysis

The different types of molecular and cellular analysis will be conducted in different laboratories of the study investigators, according to the specific expertise developed in each research centre/laboratory.

Moreover, due to the increasing international nature of scientific collaborations, this project may be done in close collaboration with industry partners, which are leading experts in providing highly specialised sample analysis. Anonymised materials may be shipped outside of the UK/Ireland and outside of Europe. If samples need to be shipped to any other than the A-STAR recruiting centres for further testing/scientific experiments, the Study Co-ordinating Centre and relevant A-STAR Consortium partners will ensure that adequate material

transfer and service level agreements are in place, before such shipments and experimental work is undertaken.

#### 8.3.3.4 Sample handling

Processing of the samples can be carried out using the laboratory manual or site-specific laboratory manuals where no instructions are given (for example when analyses are specific to one particular centre). Sample collection, processing and shipment requirements are detailed in a laboratory manual, which will be provided to participating sites.

All samples will be labelled with a unique ID and initials in an anonymised form. The anonymised samples will be used in the study described in this protocol. No identifiable documents or labels will be sent with the samples.

If samples are used in future studies not covered by the present research proposal, the approval of the Research Ethics Committee will be sought.

## 8.4 Loss to follow-up

If any of the study participants are lost to follow up contact will initially be attempted through the PI or designated research staff at each centre. If the lead investigator at the study participating centre is not the participant's usual clinician responsible for their specialist care then follow up will also be attempted through this latter clinician. A final option will be for the Study Co-ordinating Centre to attempt if patient has provided contact details and consent to be contacted. Where possible, information on the reason for loss to follow up will be recorded.

## 8.5 Auditing of study conduct and research governance

The following coordinated program will ensure quality control:

- a. Training of staff including a program of training for research nurses/investigators in severity scoring and how to use the data entry platform will be provided by the Study Co-ordinating Centre.
- b. An on-line manual on the use of the data entry platform will be provided to all study teams.
- c. Quality checks on data entry will be performed centrally (e.g. with regard to data completeness, data entry errors and inconsistencies).
- d. Selected serious adverse events (SAEs) will be checked against a set of predefined validation criteria.
- e. On-site monitoring visits as per the Study Monitoring Plan.

## 8.6 Study closure

In the first instance, the study will be running for three years. However, sufficient financial resources permitting, we anticipate that recruitment and follow up will continue well beyond this time point. Premature study closure will be down to the discretion of the Steering Committee (SC), and ongoing clinical care will be at the discretion of the treating clinician. The definition of End of Study will be when all patients have discontinued and database is locked.

#### 9 STATISTICAL CONSIDERATIONS

## 9.1 Primary endpoints

Change in disease severity between baseline and three months into treatment (V3), comparing the different treatment modalities with each other, using the EASI (Eczema Area and Severity Index).

## 9.2 Secondary endpoints

- 1. Change in EASI between baseline and six and twelve months in the different treatment groups
- 2. Change in POEM (Patient Oriented Eczema Measure) score, IGA (Investigator's Global Assessment) and quality of life (DLQI/CDLQI/IDQOL) between baseline and three months, six months and one year in the different treatment groups
- 3. Impact of *FLG* genotype on treatment effectiveness between baseline and three, six, and twelve months
- 4. Comparison of the drug adverse event profiles of all treatment groups (pharmacovigilance component of the study)

## 9.3 Sample size calculation

#### Treatment effectiveness:

Based on the results of the paediatric and adult severe AE treatment surveys we conducted in the UK [24], we expected that at least 200 patients on conventional systemic treatments needed to be recruited within 2 years and followed up for at least 12 months; 40% (80) of patients are expected to be on azathioprine, 35% (70) of ciclosporin, and 24% (50) on methotrexate. This takes a 10% loss to follow up into account. Should the pharmaceutical industry decide to support the A-STAR project financially, then we hope to be able to collect one year follow up data on patients on dupilumab during the life-time of this award.

Under these patient number assumptions, all comparisons of the EASI score (azathioprine vs ciclosporin, azathioprine vs methotrexate, ciclosporin vs methotrexate and dupilumab vs each of the other drugs) are able to detect differences that are below the published minimal clinically important difference (MCID) for each drug with high power (95%) [25]. Differences that can be detected are shown below alongside the MCIDs. Hence, with the projected patient numbers we will be able to detect differences between groups that are clinically meaningful.

	EASI score					
Comparison	Difference detectable with 95% power and expected sample sizes	Comparison	Difference detectable with 95% power and expected sample sizes	MCID		
AZA vs CsA	3.5	AZA vs Dup	3.2	6.6		
AZA vs MTX	3.9	MTX vs Dup	3.7	6.6		
CsA vs MTX	4.0	CsA vs Dup	3.3	6.6		

#### Treatment safety (pharmacovigilance):

Although we will not have adequate statistical power for a comparative analysis of rare and long-term latent adverse events of the different agents within the confines of this three-year project due to the relatively small patient numbers and short follow-up period, we will still be able to conduct a meaningful descriptive analysis of more common adverse events collected over an at least one-year period for each treatment modality.

The initial analyses will consist of comparisons in baseline status between the individuals in the treatment cohorts. For the purposes of analysis (initially) follow-up time will be censored in both cohorts if there is switching to another class of biologic therapy and censored in the standard therapy group if there is switching to a biologic agent. The adverse events of interest are calculated per person time of follow-up, after the start of therapy.

Sample size of the novel biologics/small molecule exposure group will be largely determined by external factors, including:

- 1) NICE technology assessments and resulting recommendations;
- 2) whether NICE indicates the need for pharmacovigilance and recommends patients are registered in our registry;
- 3) funding of by NHS, and
- 4) uptake by prescribing dermatologists.

The size of the comparison cohort will be more under our control. However, it is difficult to anticipate the magnitude of rate differences for adverse events between the cohorts as patients from all groups are likely to have had prior exposure to immunosuppressive drugs.

Assuming i) the risk of adverse event is proportional to the length of exposure with equal risk per year (note this may not be so), ii) power of 80%, and iii) a significance level of 5%, the following applies:

Annual adverse	Rate ratio	Person years exposure
event rate		per group
1/10,000	2	235,508
1/1000	2	23,590
2/1000	2	11,817
1/100	2	2,321
2/100	2	1,146
4/100	2	551
5/100	2	437
10/100	2	201

For guidance, the estimated risk of certain adverse events are as follows:

Squamous cell carcinoma with ciclosporin use 1 in 320 Non-melanoma skin cancer 1 in 1,000 Melanoma in high dose PUVA (phototherapy) 1 in 1,666 Melanoma in normal person 1 in 10,000

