#### 5 STUDY DESIGN

This is an observational register study of adult and paediatric patients with atopic eczema requiring systemic immune-modulatory therapy, either conventional systemic immuno-suppressive treatments (excluding oral corticosteroids) or a novel biologic or small molecule treatment.

Dupilumab has recently received approval from the EMA and FDA and other biologics and small molecules are being tested in clinical trials.

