#### Baseline 2 (Baseline 3, Baseline 4, etc.) - If switching/restarting systemic treatment

If during participation in the study a patient starts a new systemic immuno-modulatory agent or restarts the same systemic treatment after a decision for discontinuation by the treating physician has been made (excluding short-term breaks in treatment), the patient will have a further 'Baseline' visit and retake all baseline assessments, with exception of family and personal medical history and collection of blood for genetic analyses. Baseline Adverse Events information will also be collected. A new signed Informed Consent will not be required but confirmation of continued consent should be documented in the medical notes. Following this new baseline, visits will be scheduled as per original schedule (Day 1, Week 4, Week 16, and so on). If a patient has simply started on a second systemic agent alongside another, then no baseline visit is required, just 3-monthly visits as per protocol.

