Patients will be followed up for as long as possible, even if they stop treatment. The following target visit windows apply: V2 + /-2 weeks (weeks 2-6), and then +/-4 weeks thereafter, i.e. V3 weeks 12-20, etc. The date of the actual visit will be recorded in the CRF. For patients participating in the bioresource, the target visit windows are reduced to: V2 + /-1 week and V3 + /-1 week with +/-2 weeks in exceptional circumstances.

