#### Adverse events/pharmacovigilance:

Drug adverse events are calculated per person time of follow up, after the start of therapy. Time-dependent regression analyses will be undertaken to compare event rates between groups, using standard multivariable analyses to reduce confounding. We will explore the use of other statistical techniques, including propensity score matching, to accommodate confounding by indication. As children and adolescents may have a different phenotype of atopic eczema compared to adults and may respond differently to systemic therapy, we will explore this further in comparative analyses.

Estimating the risk of rare adverse effects with a smaller signal, especially lymphoma will be facilitated by long-term linkage to the national cancer registry (in addition to the control group). The risk window for cancer being defined as once exposed always at risk. Where two biologicals have been used, the proportion of time spent on each will define its possible contribution to risk. Where the adverse event is rare or where a biological intervention is under-represented in the register, the numbers of patient's data can also potentially be increased by sharing data with other compatible registers such as those operating in Germany, Italy, Spain, France, Denmark, and the Netherlands.

The aim in the long-term is to recruit at least 4,000 patients on conventional treatments and also at least 2,000 on each biological intervention (depending on the uptake of these drugs in clinical practice). 4,000 patients in

each cohort, biologicals and conventional treatment would give an exposure of 12,000 patient years in each group. This would give power to detect at least a 3- or 4-fold increase in risk of events occurring at a frequency of 1 in a 1000 or 1 in 2000 patients. Rarer events would be detected if the relative risks were higher.

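### Adverse-event rates are defined on all follow-up after the start of therapy and are cut only at switches to biologics, so off-drug time and other switches enter each drug's rate

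*Protocol*

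**What the plan says.** **Denominator.** Protocol 9.3, Treatment safety: "The adverse events of interest are calculated per person time of follow-up, after the start of therapy". Protocol 9.4, Adverse events/pharmacovigilance: "Drug adverse events are calculated per person time of follow up, after the start of therapy".

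**Censoring for safety (9.3).** Two triggers are named, as an initial approach: "follow-up time will be censored in both cohorts if there is switching to another class of biologic therapy", and time is "censored in the standard therapy group if there is switching to a biologic agent". Stopping treatment is not a trigger. Section 7.6 adds censoring at entry into a blinded trial, and withdrawal (7.4.2) also ends data collection.

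**Follow-up off drug.** Section 7.3: "Patients will be followed up for as long as possible, even if they stop treatment", with six-monthly visits once treatment has stopped. Section 7.4.2 says that stopping therapy is no reason to withdraw, and 10.7 has adverse events recorded from treatment start until withdrawal from the study.

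**Cohorts.** Section 5 describes patients on conventional systemics "or a novel biologic or small molecule treatment", and 9.3 names biologics and small molecules as one exposure group. The effectiveness paragraph of 9.4 censors the standard cohort at a move to any other systemic drug.

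**Cancer (9.4).** "The risk window for cancer being defined as once exposed always at risk". Where two biologicals were used, risk is apportioned by time on each.

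**The concern.** For acute events such as serious infection, the risk of interest is the risk while exposed. The protocol fixes a denominator that starts with therapy and, by its own censoring rule, does not stop when therapy stops. A drug's rate then depends on how long patients are followed after stopping as well as on its safety, and two drugs can differ only because their courses differ in length.

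The switch rule has a related gap. A standard-therapy patient who moves to a small molecule is not censored on the literal wording, although 9.3 puts small molecules in the novel-agent group. A patient who changes from one conventional drug to another is not censored either.

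Comparing adverse-event profiles across all treatment groups is secondary endpoint 4 in 9.2, and pharmacovigilance is a stated objective of the register (3.3).

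**Working it through.** **1. Reproduce the power table in 9.3.** Stated inputs: rate ratio 2, power 80%, significance 5% (sidedness not stated; two-sided fits). The pooled two-proportion formula, treating each person-year as one unit, is

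n = [1.960·√(2p̄(1−p̄)) + 0.842·√(p₁(1−p₁) + p₂(1−p₂))]² / (p₂−p₁)²

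| Annual rate | Stated person-years | Recomputed |
|---|---|---|
| 1/10,000 | 235,508 | 235,430 |
| 1/1000 | 23,590 | 23,511 |
| 2/1000 | 11,817 | 11,737 |
| 1/100 | 2,321 | 2,319 |
| 2/100 | 1,146 | 1,141 |
| 4/100 | 551 | 553 |
| 5/100 | 437 | 435 |
| 10/100 | 201 | 199 |

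The arithmetic is sound. But the table counts person-years of exposure and assumes risk proportional to length of exposure. Section 9.4 does the same when it turns 4,000 patients into 12,000 patient-years of exposure (12,000 / 4,000 = 3 years each). The rate definition counts follow-up.

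**2. Dilution by off-drug time.** Assumptions: comparator rate r = 1/100, on-drug rate 2r, off-drug rate r, and a share f of the exposed cohort's follow-up off drug. The protocol gives no value for f, so 10% to 50% is shown.

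Observed rate = (1−f)·2r + f·r = r(2−f), so the observed ratio is 2−f.

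| f | Observed ratio | Power at 2,321 per group | Person-years for 80% power |
|---|---|---|---|
| 0 | 2.0 | 80% | 2,319 |
| 10% | 1.9 | 72.7% | 2,769 |
| 20% | 1.8 | 64.1% | 3,385 |
| 30% | 1.7 | 54.2% | 4,266 |
| 50% | 1.5 | 33.5% | 7,750 |

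Worked line for f = 50%: p₁ = 0.010, p₂ = 0.015, p̄ = 0.0125. Then √(2·0.0125·0.9875) = 0.1571, times 1.960 = 0.3080. Also √(0.0099 + 0.014775) = 0.1571, and √2,321 × 0.005 = 0.2409. So z = (0.2409 − 0.3080)/0.1571 = −0.43, which gives a power of 33.5%.

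**3. Sensitivity to the off-drug rate.** Now let both cohorts have the same off-drug share. If off-drug risk is half the comparator's on-drug rate, f of 10% to 50% gives ratios of 1.95 to 1.67 and power of 74.2% to 40.2%. If off-drug risk is zero, the ratio stays at 2 but both rates shrink, and power is 75.7% to 50.6%. The size of the ratio bias therefore depends on the off-drug risk. Power falls in every case shown.

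**4. Unequal time on drug.** Assume two drugs with the same on-drug rate of 4/100 and off-drug rate of 2/100. On drug for 90% and 70% of follow-up, they show 3.8 and 3.4 per 100, a spurious ratio of 1.12. On drug for 90% and one third, they show 3.8 and 2.67, a ratio of 1.43.

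**5. Uncensored switches.** Assume that a share g of standard-cohort time is spent on a novel agent at the doubled rate. The ratio is 0.02/[0.01(1+g)]. For g = 10%, 20% and 30% it is 1.82, 1.67 and 1.54, with power at 2,321 person-years of 69.9%, 58.4% and 46.5%.

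**The case against.** The strongest reply is that the phrase about the start of therapy fixes only when the clock starts. The exposure-based power table, the special ever-exposed window for cancer, and the collection of on-drug status at onset and date of last treatment (8.2) all suggest that exposed time was intended. Risk windows and exposure coding are often left to a statistical analysis plan. Part of this stands: the intention may well be right. But the protocol states a denominator twice and gives explicit censoring triggers without stopping, so an analysis plan using on-drug time would depart from its text.

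Several stronger readings are tempting but not supported:

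- **Add-on drugs.** A reader might infer that combination-therapy events are charged to the first drug. Section 7.2 says only "If a patient has simply started on a second systemic agent alongside another, then no baseline visit is required". That is a visit rule, and nothing assigns the events.
- **Cancer.** A reader might see a flat contradiction between ever-exposed attribution and censoring at a switch. The censoring is labelled initial, and apportioning between two biologicals presupposes follow-up past a switch. The cancer window looks deliberate and needs only an explicit exemption.
- **Small molecules.** The word biologic in 9.3 may be shorthand, and the 9.4 paragraph with the wider rule lists adverse events among its analyses, though its heading is effectiveness. What stands is that the two rules differ.
- **Regression.** The time-dependent regression in 9.4 could carry on/off exposure. The protocol does not say that it will.
- **Direction.** Short-course drugs need not look safer: late events after stopping could push the other way.

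Section 9.3 also disclaims power for comparing rare and latent events within the three-year project and plans description of common ones. That limits the consequence for early reports but not for the long-term comparison.

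**Conclusion.** The point holds for non-malignant events. Followed literally, 9.3 and 9.4 put off-drug time into each drug's rate, which does not match the exposure basis of the protocol's own power table. The safety switch rule also leaves moves to small molecules and between conventional drugs uncensored.

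The sizes in the working are illustrations over assumed ranges of off-drug time, off-drug risk and uncensored switching, because the documents give none of these. The textual mismatch does not depend on them. The power table is arithmetically correct, and the cancer window is not in dispute.

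**What to change.** - **Non-malignant events.** Define the main analysis on on-drug person-time plus a pre-specified lag, ending at stop or switch. Enter exposure as a time-varying covariate in the planned time-dependent regression, with combination-therapy time as its own category. Keep rates over all follow-up as a sensitivity analysis.
- **Switch rule.** Align the safety wording in 9.3 with the wider rule in 9.4, so that a move to any other systemic drug, small molecules included, ends time on the original drug.
- **Malignancy.** State that the 9.3 switch censoring does not apply, and keep the ever-exposed window and the apportioning rule in 9.4.

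No new data are needed: changes in systemic therapy are reviewed at each visit (7.3), and on-drug status at onset and date of last treatment are recorded with each event (8.2). The cost is protocol wording and fewer person-years in the main analysis of acute events.
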